2 LIST OF ABBREVIATIONS

Abbreviations	Expansion
AE	adverse event
AS	acute sinusitis
CFR	Code of Federal Regulations
CI	confidence interval
COPD	chronic obstructive pulmonary disease
CRA	clinical research associate
CRF	case report form
CS	chronic sinusitis
CSF	cerebrospinal fluid
CSR	clinical study report
CT	computed tomography
EDC	electronic data capture
e.g.	‘exempli gratia’ in Latin, meaning ‘for example’
ESS	endoscopic sinus surgery
et al	‘et alia’ in Latin, meaning ‘and others’
FDA	Food and Drug Administration
GCP	good clinical practice
HIV	human immunodeficiency virus
ICF	informed consent form
ICH	International Council on Harmonisation
i.e.	‘id est’ in Latin, meaning ‘that is’
INCS	intranasal corticosteroids
IRB	institutional review board
IUD	intrauterine device
MFNS	mometasone furoate nasal spray
MRI	magnetic resonance imaging
RESS	repeat endoscopic sinus surgery
SAE	serious adverse event
SAP	statistical analysis plan
SD	standard deviation
SNOT-22	sino-nasal outcome test (22 items)
SOP	standard operating procedure
SUSAR	suspected unexpected serious adverse reaction
TEAE	treatment emergent adverse event
UADE	unanticipated adverse device effect

3 DEFINITIONS OF TERMS

Term	Definition
Acute sinusitis (AS)	Per the 2016 “International Consensus Statement on Allergy and Rhinology” definition, patient must have inflammation lasting < 4 weeks associated with the sudden onset of symptoms such as nasal blockage/obstruction/congestion or nasal discharge (anterior/posterior) and facial pain/pressure or reduction/loss of smell.
Adverse event (AE)	Any untoward medical occurrence associated with the use of a drug in humans, whether or not considered drug related. [21 CFR 312; BN ES ISO14155]
Adhesion grading scale	Adhesion severity graded on a 5-point scale from 0 to 4 at the screening and baseline visits, as follows: 0: None 1: Small but non-obstructing (no separation required) 2: Obstructing, but easily separated 3: Dense and obstructing, separation difficult 4: Severe: complete adhesion of the middle turbinate to the lateral nasal wall
Bilateral polyp grade	Sum of left and right polyp grades (see - scale below), resulting in a bilateral polyp grade of 0 to 8
Case report form (CRF)	Standardized forms designed to capture monitored data as required by the protocol.
Chronic rhinosinusitis with nasal polyps	Per the 2016 “International Consensus Statement on Allergy and Rhinology” definition, patient must have ≥ 12 weeks of: 
 • Two or more of the following symptoms: 
 ○ Mucopurulent discharge (rhinorrhea or postnasal drip) ○ Nasal obstruction and congestion ○ Decreased/absent sense of smell ○ Facial pressure/pain • And one or more of the following findings: 
 ○ Evidence of inflammation on paranasal sinus examination or computed tomography ○ Evidence of purulence coming from paranasal sinuses or ostiomeatal complex • And presence of polyps.
Enrolled	Subjects are considered enrolled upon signing the informed consent form.
High-dose steroids	The following steroids are considered as high-dose in the study: oral, parenteral, injections, budesonide or other sinus steroid irrigations, rinses or drops, nebulized steroids administered nasally.
Implant delivery success	Successful deployment of the S8 Sinus Implant to the target site. Deployment is considered successful if the procedure concludes with a successful placement in the target sinus, even if a second attempt is required. Implant delivery success rate is calculated as proportion of successful deployments of the S8 Sinus Implant to the target site per total number of sinuses attempted including the baseline and repeat placement procedures.

Term	Definition
Malfunction	Failure of an investigational medical device to perform in accordance with its intended purpose when used in accordance with the instruction for use or clinical investigation plan. [BS EN ISO14155] Failure of a device to meet its performance specifications or otherwise perform as intended. Performance specifications include all claims made in the labeling for the device. The intended performance of a device refers to the intended use for which the device is labeled or marketed. [21CFR 803]
Nasal obstruction/congestion scale	A 4-point scale defined as follows: 0: No symptoms 1: Mild symptoms, clearly present but minimal awareness and easily tolerated 2: Moderate symptoms, definite awareness of symptoms that is bothersome but tolerable 3: Severe symptoms, hard to tolerate, cause interference with activities or daily living
Percent ethmoid sinus obstruction	Estimated visually based on endoscopic examination on a scale ranging from 0% (no obstruction) to 100% (complete obstruction of the ethmoid cavity by polyps, edema and/or scarring).
Polyp grading scale	Polyps are assessed endoscopically and graded on an 8-point scale ranging from 0 to 4 defined as follows: 0: No visible sinonasal polyps 1: Small amount of sinonasal polyps confined in middle meatus 1.5: Small amount of sinonasal polyps confined in middle meatus with expanded amount of polypoid edema obstructing $\geq 25\%$ of the ethmoid sinus cavity 2: Expanded amount of sinonasal polyps confined in middle meatus 2.5: Expanded amount of sinonasal polyps confined in middle meatus with expanded amount of polypoid edema obstructing $\geq 50\%$ of the ethmoid sinus cavity 3: Sinonasal polyps extending beyond middle meatus but not totally obstructing the nasal cavity 3.5: Sinonasal polyps extending beyond middle meatus with expanded amount of polypoid edema obstructing $\geq 75\%$ of the ethmoid sinus cavity 4: Sinonasal polyps extending beyond middle meatus and completely obstructing the nasal cavity
Serious adverse event (SAE) or serious suspected adverse reaction (SSAR)	Adverse events are considered “serious” if, in the view of either the investigator or sponsor, they result in any the following outcomes: 
 • Death; or • A life-threatening adverse event; or • Inpatient hospitalization or prolongation of existing hospitalization; or

Term	Definition
	
 • A persistent or significant incapacity or substantial disruption of the ability to conduct normal life functions; or • A congenital anomaly/birth defect. 
Important medical events that may not result in death, be life-threatening, or require hospitalization may be considered serious when, based upon appropriate medical judgment, they may jeopardize the patient and may require medical or surgical intervention to prevent one of the outcomes listed in this definition. [21 CFR 312]

Suspected unexpected serious adverse reaction (SUSAR)	Any SSAR that is unexpected. [21 CFR 312]
Suspected adverse reaction (SAR)	Any AE for which there is a reasonable possibility that the drug caused the AE. Reasonable possibility means there is evidence to suggest a causal relationship between the drug and the adverse event. Suspected adverse reaction (SAR) implies a lesser degree of certainty about causality than adverse reaction, which means any adverse event caused by a drug. [21 CFR 312]
Sino-Nasal Outcome Test (SNOT-22)	
A validated, disease-specific, symptom-scoring instrument consisting of 22 questions, each scored on a scale of 0 to 5 defined as follows:
 
 0: No problem 1: Very mild problem 2: Mild or slight problem 3: Moderate problem 4: Severe problem 5: Problem as bad as it can be
Source data	All information in original records and certified copies of original records of clinical findings, observations, or other activities in a clinical trial necessary for the reconstruction and evaluation of the trial.
Source documents	Original documents, data, and records. Printed, optical or electronic document containing source data.
Subject	An individual who participates in a clinical investigation.
Treatment emergent adverse event (TEAE)	Any event not present prior to the treatment or an event already present that worsens either in intensity or frequency following the treatment.
Unanticipated Adverse Device Effect (UADE)	Any serious adverse effect on health or safety or any life-threatening problem or death caused by, or associated with, a device, if that effect, problem, or death was not previously identified in nature, severity, or degree of incidence in the investigational plan or application, or any other unanticipated serious problem associated with a device that relates to the rights, safety, or welfare of subjects. [BS EN ISO 14155]
Unanticipated Serious Adverse Device Effect (USADE)	Any serious adverse device effect which by its nature, incidence, severity or outcome has not been identified in the current version of the risk analysis report. [21 CFR 812]
Unexpected adverse event or suspected adverse reaction	An AE/SAR is considered 'unexpected' if it is not listed in the investigator brochure or is not listed at the specificity or severity that has been observed. Unexpected events also refer to AE/SARs that are mentioned in the investigator brochure as occurring with a class of product or as anticipated from the pharmacological properties of the

Term	Definition
	product, but are not specifically mentioned as occurring with the particular investigational product. [21 CFR 312]

4 PROTOCOL SUMMARY

Study Title	The ENCORE Study: Safety Evaluation of Repeat Placement of the Corticosteroid-Releasing S8 Sinus Implant in Chronic Sinusitis Patients with Nasal Polyps
Objective	To assess the safety of repeat placement of the S8 Sinus Implant when used in chronic sinusitis (CS) patients with recurrent nasal polyps
Investigational Product	
The S8 Sinus Implant (mometasone furoate, 1350 mcg) is a bioabsorbable, corticosteroid-eluting implant studied for the treatment of nasal polyps in patients ≥ 18 years of age who have had ethmoid sinus surgery.
 
The S8 Sinus Implant is placed in the ethmoid sinus under endoscopic visualization. The implant may be left in the sinus to gradually release the corticosteroid over approximately 90 days. The implant must be removed by 90 days after placement or may be removed earlier at the investigator's discretion, using standard surgical instruments.

Study Design	
A prospective, non-randomized, open-label, multicenter clinical trial, consisting of three phases:
 
Screening
 
 • Patients who sign the institutional-review board (IRB) approved informed consent form will be considered enrolled into the study. • All consented subjects will undergo a screening assessment consisting of an endoscopic examination. 
Baseline/Procedure
 
 • Eligible subjects will undergo a baseline assessment. • Subject meeting all eligibility criteria will undergo an in-office bilateral placement of the S8 Sinus Implant in the ethmoid sinuses. 
Follow-up
 
 • Subjects will return for 7 follow-up visits at Days 30, 60, 90, 120, 150, 180 and 365. • At the Day 90 visit, subjects will undergo repeat in-office placement of the S8 Sinus Implant in each ethmoid sinus with nasal polyps (grade ≥ 1). Repeat placement will not be performed if polyp grade is < 1, or if the subject declines the procedure.
Subject Enrollment	A total of 50 subjects will be treated at up to 10 study centers across the U.S. with a maximum of 15 treated subjects at a single center.
Study Population	Patients ≥ 18 years of age with CS who have undergone prior endoscopic sinus surgery (ESS), including bilateral total ethmoidectomy, and present with bilateral ethmoid polyposis, and in whom bilateral placement of the S8 Sinus Implant is both feasible and medically appropriate.

[figure not shown]

Eligibility Criteria
	
Key inclusion criteria:
 
 • Confirmed diagnosis of CS with nasal polyps. Per the 2016, “International Consensus Statement on Allergy and Rhinology” definition, patient must have ≥ 12 weeks of: 
 ○ Two or more of the following symptoms: 
 ▪ Mucopurulent discharge (rhinorrhea or postnasal drip) ▪ Nasal obstruction and congestion ▪ Decreased/absent sense of smell ▪ Facial pressure/pain ○ And one or more of the following findings: 
 ▪ Evidence of inflammation on paranasal sinus examination or computed tomography ▪ Evidence of purulence coming from paranasal sinuses or ostiomeatal complex ○ And presence of polyps. • Previous ESS including bilateral total ethmoidectomy at least 90 days prior to screening. • Patient must have evidence of bilateral ethmoid sinus polyps (grade ≥ 2 on each side) • Ethmoid sinus anatomy is amenable to bilateral placement of the S8 Sinus Implant (20 mm nominal length, 7 mm compressed diameter) 
Key exclusion criteria:
 
 • Extensive ethmoid sinus polyps (grade 4 on at least one side) • Extensive adhesions/synechiae (grade 3 or 4) • Oral-steroid dependent condition • History of allergy or intolerance to corticosteroids or mometasone furoate • Physical obstruction that would preclude access to or placement of the S8 Sinus Implant in the middle meatus • Evidence of acute sinusitis (AS), invasive fungal sinusitis or another disease or condition expected to compromise survival or ability to complete assessments during the 180-day follow-up period • Use of parenteral and injected steroids (e.g., Kenalog injection) 30 days prior to the baseline procedure • Use of monoclonal antibodies (e.g., Dupoxent, Nucala, Xolair) for treatment for asthma, allergies or nasal polyps 30 days prior to the baseline procedure
------------------------------------	--

	
 Use of oral steroids, budesonide or other sinus steroid irrigations/rinses, nebulized steroids administered nasally or budesonide drops 14 days prior to the baseline procedure
Safety Evaluation	
All adverse events reported by subjects between consent and the Day 365 follow-up visit (end of study) will be tabulated.
 
Each adverse event will be evaluated by investigators in terms of seriousness, severity (i.e., mild, moderate, severe) and strength of relationship (i.e., not related, unlikely related, possibly related, related) to study drug, study device, and implant procedure.

Efficacy Endpoints	
Patient-reported endpoints:
 
 Change from baseline to each time-point (Days 30, 60, 90, 120, 150, 180) in the mean nasal obstruction/congestion score (scale 0 to 3) based on a reflective questionnaire Change from baseline to each time-point (Days 30, 60, 90, 120, 150, 180) in SNOT-22 total score (scale 0 to 110), domain scores and individual symptom scores (scale 0 to 5) 
Endoscopic endpoints:
 
 Change from baseline to each time-point (Days 30, 60, 90, 120, 150, 180) in bilateral polyp grade (scale 0 to 8) Change from baseline to each time-point (Days 30, 60, 90, 120, 150, 180) in ethmoid sinus obstruction (scale 0% to 100%)
Other Endpoints	
Implant delivery success rate:
 
 Proportion of successful deployments of the S8 Sinus Implant to the target site including the baseline and repeat placement procedures. See Section 3 Definition of terms 
Interventions received:
 
 Proportion of subjects who received interventions (i.e., sinus-related medications, systemic steroid interventions, surgical interventions for sinusitis) through Day 365
Concomitant Medications	
 After the baseline procedure, subjects will be encouraged to use saline rinses regularly through Day 365. After the baseline procedure, subjects will be required to use MFNS 200 mcg (two sprays in each nostril) once daily throughout the whole duration of the follow-up, unless the use of MFNS is not warranted clinically. Both the generic version of MFNS by Apotex or Novartis and the brand-name version by Merck (Nasonex) can be used. High-dose steroids (e.g., oral, parenteral, injections, budesonide or other sinus steroid irrigations/rinses or drops, nebulized steroids administered nasally) will be allowed during the study

	
follow-up only if clinically necessary. (see Medical and Surgical Interventions)
 
 • Orally-inhaled steroids for control of asthma will be permitted. • If infection is suspected at any time during the study, treatment with antibiotics will be permitted. • Use of monoclonal antibodies is prohibited throughout the 365-day follow-up period. • To the extent possible, subjects will be maintained on stable regimens of leukotriene inhibitors and/or immunotherapy for allergies, if currently on such regimens; however, use of breath-powered or other methods of intranasal steroid delivery for allergies is not permitted during the study. • Use of drug-eluting implants (PROPEL[®], PROPEL[®] Mini, PROPEL[®] Contour) is prohibited during the baseline procedure and throughout the 365-day follow-up unless placed immediately following repeat ESS performed in the operating room setting.

Medical and Surgical Interventions
	
Medical interventions:
 
 • During the study follow-up, high-dose steroids (e.g., oral, parenteral, injection, budesonide or other sinus steroid irrigations, rinses or drops, nebulized steroids administered nasally) may be used as a medical intervention in cases where a clinically significant increase or persistence in ethmoid sinus polyposis occurs, leading to subject seeking intervention. • High-dose steroids may be used for reasons other than ethmoid sinus obstruction, if medically necessary. • In either case, high-dose steroid interventions and reasons of their use will be recorded on the concomitant medication and follow-up case report forms (CRF). 
Surgical interventions:
 
 • During the study follow-up, surgical intervention (e.g., repeat ESS, office polypectomy) may be required in cases where a clinically significant increase or persistence in ethmoid sinus polyposis occurs.

Follow-up
	
Each subject will return for 7 follow-up visits:
 
 • Day 30 (± 7 days) • Day 60 (± 7 days) • Day 90 (± 7 days) implant removal & repeat placement • Day 120 (± 7 days) • Day 150 (± 7 days) • Day 180 (± 14 days) implant removal • Day 365 (± 14 days)

	Subjects may come in for additional unscheduled office visits if necessary. Circumstances that may warrant additional visits include, but are not limited to worsening of sinus symptoms, sinus-related adverse events requiring medical evaluation, and implant migration.
Study Duration	The anticipated timeline for this study is as follows: 
• Enrollment start: November 2017• Enrollment end: January 2018• Follow-up end: November 2018
Duration of Study Period (per subject)	Screening visit (1 day) + baseline/procedure (1 day) + follow-up (365 days) = Approximately 367 days

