10.3 Subject Withdrawal

Study subject may be withdrawn or terminated for the following reasons:

- Subject death
- Concomitant disease or any disease or condition that makes further study participation impossible (but without relationship to the investigational product).
- Subject voluntarily chooses not to participate further in the study. If withdrawal takes place after baseline procedure, the implants will be removed, if still present.
- Subject's non-compliance with study procedures.
- Lost to follow-up: the subject is more than 30 days late to a study visit and three documented attempts to contact the subject are unsuccessful. A subject who misses a study visit should be contacted by site personnel to determine the reason for the missed visit, which should be documented in the subject's study records. Note: A subject who misses a study visit but attends a subsequent visit will no longer be considered lost to follow-up.
- In the investigators's opinion, a significant safety concern arises that requires subject discontinuation.
- In the investigators's opinion, it is not in the best interest of the subject to continue study participation. The implants will be removed, if still present.

If a subject decides to withdraw from the study, every attempt should be made to continue to collect safety data in the patient's medical records. Data collected up to the point of subject withdrawal or termination will be maintained in the study database and included in analyses as appropriate.

All enrolled subjects, including those withdrawn or lost to follow-up, will be accounted for and documented.

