12 CONCOMITANT MEDICATION

The study standardized medication regimen will be as follows:

- Leading up to the baseline procedure, there is a 30-day restriction for use of parenteral and injected steroids (e.g., Kenalog injection), and monoclonal antibodies (e.g., Dupixent, Nucala, Xolair) 1
- Leading up to the baseline procedure, a 14-day restriction for use of oral steroids, budesonide or other sinus steroid irrigations/rinses, nebulized steroids administered nasally or budesonide drops.
- After the baseline procedure, subjects will be encouraged to use saline rinses regularly through Day 365.
- After the baseline procedure, subjects will be required to use MFNS 200 mcg (two sprays in each nostril) once daily throughout the entire duration of the follow-up, unless the use of MFNS is not warranted clinically. Both the generic version of MFNS by Apotex or Novartis and the brand-name version by Merck (Nasonex) can be used.
- High-dose steroids (e.g., oral, parenteral, injections, budesonide or other sinus steroid irrigations, rinses or drops, nebulized steroids administered nasally) will be allowed during the study follow-up only if clinically necessary (see Section 13 *Medical and Surgical Interventions*).
- Orally-inhaled steroids for control of asthma will be permitted.
- If infection is suspected at any time during the study, treatment with antibiotics will be permitted.

- Use of monoclonal antibodies is prohibited during the 365-day follow-up period.
- To the extent possible, subjects will be maintained on stable regimens of leukotriene inhibitors and/or immunotherapy (e.g., Montelukast, Zafirleukast, Zileuton) for allergies through Day 365, if currently on such regimens; however, use of breath-powered or other methods of intranasal steroid delivery for allergies is not permitted during the study.
- Use of drug-eluting implants (PROPEL[®], PROPEL[®] Mini, PROPEL[®] Contour) is prohibited during the baseline procedure and throughout the 365-day follow-up period, unless placed immediately following RESS performed in the operating room setting.

All sinus-related and AE-related medications will be recorded in EDC, including their full brand/trade or generic names (whichever prescribed), dose, frequency, indication, start and end dates. Each AE will be coded using the Medical Dictionary for Regulatory Activities (MedDRA) and presented based on the system organ class (SOC) and preferred term.

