5.0 ANALYSIS POPULATION

All analyses are conducted using the safety population, which is defined as all subjects and sinuses that actually received the S8 Sinus Implant in target sinuses at baseline/procedure.

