7.3 Medical or Surgical Interventions

Since high-dose steroids (e.g., oral, parenteral, injection, budesonide or other sinus steroid irrigations, rinses or drops, nebulized steroids administered nasally) or surgical intervention may confound the efficacy measures, the following method will be applied to the analyses in cases where such interventions are performed:

- If a subject initiates high-dose steroids (see Clinical Study Protocol Appendix A for a list of medications considered as high-dose steroids) or undergoes polypectomy or revision ESS for chronic sinusitis conditions attributable to the ethmoid sinus during the study, this represents treatment failure.
- For subjects with interventions for treatment failure occurring at any time point through Day 180 (regardless of receiving repeat implant placement at Day 90), the last available scores for Nasal Obstruction/Congestion, SNOT-22, and endoscopic measures prior to interventions will be carried forward to all time points through Day 180 or the last follow-up visit.

No other data imputation rules will be applied in the planned statistical analyses. All efficacy endpoints will be presented as intervention-adjusted values.

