7.4 Efficacy and Other Endpoints

Continuous measures are analyzed using descriptive statistics such as means, medians, and SD. and, where appropriate, 95% CI for the mean assuming a normal distribution.

Continuous measures include:

- Nasal Obstruction/Congestion score: Change from baseline to each time-point (Days 30, 60, 90, 120, 150, 180) in the mean score (scale 0 to 3)
- SNOT-22 score: Change from baseline to each time-point (Days 30, 60, 90, 120, 150, 180) in SNOT-22 total score, domain scores, and individual symptom scores. The total score of SNOT-22 is calculated as the sum of all items, and ranges from 0 to 110 with the highest score representing worsening. The following table lists corresponding items and ranges for each symptom domain.

SNOT-22 Domains	Survey Items	Score Range
Rhinologic Symptoms	#1, #2, #3, #6, #21, #22	0–30
Extra-Nasal Rhinologic Symptoms	#4, #5, #6	0–15
Ear/Facial Symptoms	#2, #7, #8, #9, #10	0–25
Psychological Dysfunction	#14, #15, #16, #17, #18, #19, #20	0–35
Sleep Dysfunction	#11, #12, #13, #14, #15	0–25

- Bilateral Polyp Grade: Change from baseline to each time-point (Days 30, 60, 90, 120, 150, 180) in bilateral polyp grade (scale 0 to 8), which represents a sum of left and right sides. The bilateral polyp grade for a given patient is set as missing if the grade for one side is missing.
- Percent Ethmoid Sinus Obstruction: Change from baseline to each time-point (Days 30, 60, 90, 120, 150, 180) in percent ethmoid sinus obstruction (scale 0% to 100%). Percent ethmoid obstruction scores on left and right sides are averaged for each subject at each time point. The results for a given patient is set as missing if the score for one side is missing.

Categorical measures are analyzed as counts, rates, proportions and frequencies. Where it is appropriate, 95% CI (computed using the exact method) and p-values will be presented.

Categorical measures include:

- Implant delivery success rate: Proportion of successful deployments of the S8 Sinus Implant to the target site per total number of sinuses attempted including the baseline and repeat placement procedures. Implant delivery success rate at Baseline, Day 90 and Baseline & Day 90 combined will be presented.

- Interventions received: Proportion of subjects who received interventions (i.e., sinus-related medications, systemic steroid interventions, and surgical interventions) through Day 365.

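### Interventions through Day 365 are planned as one crude proportion of all implanted subjects, so the rescue rate is understated if anyone leaves early unrescued; a censored estimate beside it is a cheap improvement

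*Protocol*

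**What the plan says.** The protocol summary lists the endpoint among its other endpoints as "Proportion of subjects who received interventions (i.e., sinus-related medications, systemic steroid interventions, surgical interventions for sinusitis) through Day 365". SAP 7.4 repeats it as "Proportion of subjects who received interventions (i.e., sinus-related medications, systemic steroid interventions, and surgical interventions) through Day 365" and places it under a general rule: "Categorical measures are analyzed as counts, rates, proportions and frequencies", with exact 95% intervals where appropriate.

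The denominator comes from SAP 5.0: "All analyses are conducted using the safety population, which is defined as all subjects and sinuses that actually received the S8 Sinus Implant" (Protocol 16.6 agrees). The only handling rule, in SAP 7.3, carries efficacy scores forward after an intervention, through Day 180. It then adds: "No other data imputation rules will be applied in the planned statistical analyses".

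Protocol 10.3 allows for early exit, including "Lost to follow-up: the subject is more than 30 days late to a study visit" with failed attempts at contact. It keeps leavers' data for use where suitable but does not say how an unrescued leaver enters this proportion. Protocol 12 records, for sinus-related medications, "dose, frequency, indication, start and end dates".

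The intervention lists differ. SAP 7.4 counts sinus-related medications, systemic steroids and surgery. SAP 4.3 counts steroids or antibiotics for any reason, polypectomy and repeat ESS.

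**The concern.** A one-year rescue rate is a cumulative risk. If it is estimated as events over everyone implanted, a subject last seen at Day 100 without rescue stays in the denominator as a success to Day 365. Events that go unseen can lower the figure but cannot raise it, so any error is in the favourable direction.

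The number matters more than its place among the other endpoints suggests. Endoscopy, the congestion score and SNOT-22 all stop at Day 180 in the schedule of assessments, and Protocol 14.1 does not count polyp persistence or formation as an adverse event. After Day 180 this proportion is the only planned summary of disease control.

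The objective is repeat placement, and SAP 7.5 divides implant-related adverse events at the Day 90 repeat procedure. The intervention figure has no such division, so it cannot show how much rescue followed re-implantation.

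**Working it through.** **The plan's own figures.** The documents state no rescue rate, dropout rate or precision target for this endpoint, so none can be reproduced. The sample-size figure does reproduce: 50 subjects × 2 = 100 baseline implants, and 100 + 85 repeat placements = 185 procedures (Protocol 16.1, SAP 7.2). Only the 50 subjects are used below.

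**Step 1: expected crude proportion.** Assumptions, none from the documents: a constant rescue hazard, exits unrelated to outcome, a true one-year risk R of 20% or 40%, and d = 5 or 10 subjects whose contact ends early, uniformly over Days 1–365 or Days 1–180.

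- Hazard: λ = −ln(1 − R)/365, which is 0.000611 per day for R = 20% and 0.001400 for R = 40%.
- Chance that a leaver is rescued before leaving: E = average of 1 − exp(−λt) over the exit days t.
- Crude proportion = (1 − d/50) × R + (d/50) × E.

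| R | Exits over | E | Crude, 5 exits (shortfall, points) | Crude, 10 exits (shortfall, points) |
|---|---|---|---|---|
| 20% | Days 1–365 | 10.4% | 19.0% (1.0) | 18.1% (1.9) |
| 20% | Days 1–180 | 5.3% | 18.5% (1.5) | 17.1% (2.9) |
| 40% | Days 1–365 | 21.8% | 38.2% (1.8) | 36.4% (3.6) |
| 40% | Days 1–180 | 11.7% | 37.2% (2.8) | 34.3% (5.7) |

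For example, R = 40% with 5 exits over the year gives 0.9 × 0.40 + 0.1 × 0.218 = 0.382. The range of 1.0 to 5.7 points is about 0.5 to 2.8 subjects in 50.

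**Step 2: a second model.** Let rescue and dropout be independent constant hazards, with time in years, λ = −ln(1 − R) and μ = −ln(1 − dropout). Crude = λ/(λ + μ) × (1 − exp(−(λ + μ))). For R from 20% to 50%, the shortfall is 0.5 to 1.1 points at 5% dropout, 1.0 to 2.3 at 10% and 2.0 to 4.6 at 20%. It is zero with no dropout.

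**Step 3: what the alternative would show.** Take 50 subjects, 3 rescued before Day 90 and 9 after, with L unrescued leavers at Day 90 (illustrative numbers).

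- Crude: 12/50 = 24.0%, exact 95% CI 13.1% to 38.2%, a width of 25.1 points.
- Kaplan-Meier: 1 − (47/50) × (1 − 9/(47 − L)). This gives 24.4%, 24.8%, 26.1% and 28.9% for L = 1, 2, 5 and 10.
- Bound with every leaver counted as rescued: (12 + L)/50 = 26%, 28%, 34% and 44%.

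The correction is small at low dropout. The bound moves much faster, so the completeness of follow-up needs to be reported too.

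**The case against.** The strongest case is that this is a descriptive figure in a single-arm safety study. It promises the proportion who received an intervention, and an observed proportion with all losses accounted for is a legitimate summary. No test, threshold or sample-size argument uses it, and the shortfall is well inside the sampling error. There are mitigations: safety data are still sought after withdrawal, rescued subjects are followed to study end, a subject who misses a visit but returns is not lost, and medications are collected at Day 365. All of this stands and sets the priority. None of it says how an unrescued leaver is counted.

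Several stronger readings are tempting but not supported:

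- **That the rate is understated, full stop.** Protocol 10.3 says that subjects may be withdrawn; it forecasts no number. With complete follow-up there is no bias. The denominator is also inferred from the general population rule, and the table mock-ups are not in the text available.
- **That it applies to any list of interventions.** Sinus-related medications, read literally, could include the daily MFNS that the protocol requires. Nearly everyone would then have an event at the start, leaving little to understate. The point holds only for the rescue components.
- **That the exact interval is centred on the wrong value.** Exact intervals are not centred on the estimate: for 24.0% the midpoint of 13.1% to 38.2% is 25.7%.
- **That Kaplan-Meier removes the bias.** If subjects doing badly are the ones who leave, censoring is informative and Kaplan-Meier is also too low; if those doing well leave, it is too high.
- **That the study calendar truncates follow-up.** The summary anticipates enrollment ending in January 2018 and follow-up in November 2018. The timeline is only anticipated, and the plan commits every subject to a Day 365 visit.

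**Conclusion.** The concern holds conditionally. As SAP 5.0, 7.3 and 7.4 read together, an unrescued early leaver is a one-year non-event, and for high-dose steroids and for polypectomy or repeat ESS this can only lower the reported rate. Under the assumptions in Step 1 the shortfall is about 1 to 6 percentage points. The top of that range needs 10 of 50 subjects to leave within 180 days and a 40% rescue risk, and neither figure comes from the documents. No inference in the trial turns on it. The missing division at Day 90 is a gap in presentation rather than a bias, and the same table would close it. This is a cheap improvement of minor priority.

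**What to change.** In SAP 7.4, before database lock:

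1. Keep the crude count and percentage.
2. For the rescue components only, add Kaplan-Meier cumulative incidence from baseline placement to the first high-dose steroid course and, separately, to the first surgical intervention, censored at last contact. Give 95% CIs and numbers at risk at Days 90, 180 and 365. Because the Day 90 visit has a window of ±7 days, the Day 90 reading only approximates the split at repeat placement.
3. State the number with complete follow-up to Day 365.
4. Give a bound that counts unrescued leavers as rescued, because censoring may be informative.
5. Reconcile the intervention lists in SAP 4.3 and 7.4 so that required MFNS is not counted as an event.
6. Confirm that the CRF captures the surgery date. Protocol 12 names start and end dates for medications only.

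The cost is one SAP paragraph and one extra table. If subjects do leave early, the reported rate becomes slightly less favourable and its interval slightly wider.
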